7.8 Estimands

7.8.1 Primary outcome estimand

Amongst hospitalised, critically ill, adult patients at risk of acute muscle wasting who do not die and do not experience limp amputation or a intracerebral event within 30 days of treatment assignment, what is mean difference in functional ability, as measured by the 30-second sit-to-stand test, 30 days after treatment assignment between 10-day ketogenic enteral feeding regimen compared with standard enteral feeding regardless of whether alternative treatment(s), rescue medication(s), incorrect treatment dose, or the opposing treatment were received or adverse event or further illness experienced. The objective is to demonstrate statistical superiority of ketogenic enteral feeding relative to standard feeding for this estimand.

Table. Estimand Framework (Primary Outcome)

Domain	Definition	Description
Target population	Patients targeted by the research objective	
Adults ≥18 years old, who don't die or experience limp amputation or a intracerebral event within 30 days of treatment assignment, admitted to hospital critical care units with:
 
 • Acute respiratory failure during first 24 hours of ICU admission; • Expected to require advanced respiratory support for >48 hours; • Evidence of inflammation, and; • Nasogastric feeding planned for >48 hours 
OR
 
 • Multi-organ failure during first 24 hours after ICU admission, and; • Nasogastric feeding planned for >48 hours
Treatment conditions	Experimental and control interventions administered to patients in different trial arms	
Intervention arm Ketogenic enteral feeding (75% Fats, 20% Protein, & 5% Carbohydrates) administered via nasogastric tube for 10 days unless no longer indicated
 
Control arm Standard enteral feeding administered hours in critical care

Endpoint	Outcome variable to be measured for each patient	via nasogastric tube for 10 days unless no longer indicated
Population- level	Quantitative measure used to compare and summarise difference between trial arms	30-second Sit-to-Stand test (i.e., the number of sit-to-stand repetitions performed in 30 seconds) 30 days after treatment assignment
summary measure		Mean difference between trial arms
Intercurrent events	Post-randomisation events that affect that measurement, interpretation, and/or existence of an outcome	Strategies to account for intercurrent events

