7.8.2 Survivor average causal effect estimand

The survivor average causal effect (SACE) analysis is a sensitivity analysis for the primary outcome analysis estimating the average treatment effect in those patients who did not and would not die.⁴⁹ Outcome truncating intercurrent events will be handled using a principal stratum intercurrent event strategy articulated in detail in the statistical analysis plan.

Table. Estimand Framework (SACE)

Domain	Definition	Description
Target population	Patients targeted by the research objective	
Adults ≥18 years old admitted to hospital critical care units with
 
 • Acute respiratory failure during first 24 hours of ICU admission; • Expected to require advanced respiratory support for >48 hours;

		
 • Evidence of inflammation, and; • Nasogastric feeding planned for >48 hours 
OR
 
 • Multi-organ failure during first 24 hours after ICU admission, and; • Nasogastric feeding planned for >48 hours
Treatment conditions	Experimental and control interventions administered to patients in different trial arms	
Intervention arm
 
Ketogenic enteral feeding (75% Fats, 20% Protein, & 5% Carbohydrates) administered via nasogastric tube for 10 days unless no longer indicated
 
Control arm
 
Standard enteral feeding administered via nasogastric tube for 10 days unless no longer indicated

Endpoint	Outcome variable to be measured for each patient	30-second Sit-to-Stand test (i.e., the number of sit-to-stand repetitions performed in 30 seconds) 30 days after treatment assignment
Population-level summary measure	Quantitative measure used to compare and summarise difference between trial arms	Mean difference between trial arms
Intercurrent events	Post-randomisation events that affect that measurement, interpretation, and/or existence of an outcome	Strategies to account for intercurrent events

• Develops adverse event & discontinues assigned treatment	Outcome-modifying event	Treatment policy
• Receives alternative treatment and continues assigned treatment	Outcome-modifying event	Treatment policy
• Takes rescue medication and discontinues assigned treatment	Outcome modifying event	Treatment policy
• Death within 30 days after treatment assignment	Outcome-truncating event	Principal stratum

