• Discontinuing intervention or control treatment before end of 10-day duration	Outcome-modifying event	Treatment policy
• Randomised treatment not received or opposing treatment received (i.e., opposite to the trial arm to which the participant was randomly allocated)	Outcome-modifying event	Treatment policy
• New events that prevent the collection of the primary outcome: - new limb amputation - new intracerebral event precluding physical function testing - other	Outcome-truncating events	Principal stratum
• New events that prevent delivery of the treatment (i.e., feeding):	Outcome-modifying events	Treatment policy

- new indication for parenteral nutrition
- patient becomes nil per oral
- other

- Receives wrong dose of intervention

Outcome-modifying

event

Treatment policy

8. Trial methodology

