9.7.1 Performing a 30-Second Sit-to-Stand Test

The 30-second sit-to-stand (30STS) test involves recording the number of stands a person can complete in 30 seconds rather than the amount of time it takes to complete a pre-determined number of repetitions. That way, it is possible to assess a wide variety of ability levels with scores ranging from 0 for those who cannot complete 1 stand to greater than 20 for more fit individuals.

The participant is encouraged to complete as many full stands as possible within 30 seconds. The participant is instructed to fully sit between each stand. While monitoring the participant's performance to ensure proper form, the tester silently counts the completion of each correct stand. The score is the total number of stands within 30 seconds (more than halfway up at the end of 30 seconds counts as a full stand). Incorrectly executed stands are not counted. The modified 30STS can be used for those unable to stand without the use of armrests, a task which many patients at point of discharge from critical care will find difficult to perform.⁶³

Prior to the trial study commencement, the research team will be given a 30-minute education session and a written protocol to facilitate the standardised and safe performance of the 30-STS test. Patients will also be asked to perform the 30STS at discharge from the critical care unit, to ensure they are familiar with the test prior to repeating it 30 days after randomisation. While it is likely that patients will still be in hospital at 30 days after randomisation (median hospital length of stay was 40 days in our pilot study), the 30STS test can also be performed via video and/or teleconferencing if patients are discharged home.^{34,65}

Whilst on the call, the tester will screen for safety using the Australia-modified Karnofsky Performance Status (AKPS \geq 50%) and the Clinical Frailty Score (CFS<6) to determine suitability for performing the 30STS in this manner.⁶⁵ This will be accompanied by a short screening questionnaire:⁶⁵

- Do you have someone at home who can supervise you while completing this test?
 - If CFS >4 and no-one to supervise test completion, do not complete the test.
- Are you wearing study shoes that don't slip and have support at the heel?
 - If "no" and no shoes are available, do not complete the test.
- Have you had a recent fall?
 - If "yes", do not complete the test.
- Are you feeling dizzy, cold, or sweaty?
 - If "yes", do not complete the test.

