12.1 Statistical analysis

The primary outcome analysis is a survivor analysis: The treatment effect is the difference in the mean 30STS among participants who survive to 30 days follow-up under intervention and control. The treatment effect will be estimated using a linear mixed effects model adjusted for site (as a random effect), age, and Functional Co-morbidity Index. The main analyses of primary and secondary outcomes will be conducted using multiple imputation under a missing at random assumption for those participants lost to follow-up. Controlled multiple imputation analysis using a δ -based imputation approach will be performed as ASiCS II Protocol v2.0 | IRAS: 356548 | 24.07.2025 | Chief Investigator: [name] Based on SOP 12a Associated document 1: JRMO Protocol template for interventional studies v5.0 02.12.2024

sensitivity analyses.⁷⁶ In this approach an offset term, δ , is added to values imputed under MAR to assess the impact of unobserved participants having a worse or better outcome than those observed. We will furthermore estimate the survivor average causal effect and assess consistency with the main primary outcome treatment effect estimate.⁴⁹

In the primary outcome analysis it is assumed that neither feeding regimen influences mortality in the population of interest so that participants who survive under ketogenic feeding and standard feeding are not inherently different and the estimated causal effect of treatment on those patients who would always survive regardless of feeding regimen is the most relevant. In support of this statement, a systematic review of 212 trials provided no conclusive evidence of any single pharmacology intervention translating to mortality benefit.⁷⁷ However, there is debate on the ability of nutritional interventions to alter mortality in critical illness, with large randomised trials of increased protein or energy not demonstrating efficacy in altering mortality.^{13,78} Mortality will be closely monitored by the DMEC and formally assessed at the end of the trial using a non-inferiority test.

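### The primary estimand drops survivors with a new amputation or intracerebral event, the primary analysis keeps all 30-day survivors, and the SACE text and table disagree on these patients

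*Protocol*

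**What the plan says.** Section 7.8.1 defines the primary estimand for patients "who do not die and do not experience limp amputation or a intracerebral event within 30 days of treatment assignment" ('limp' is read here as limb). The same sentence then says the effect is wanted whatever adverse event or later illness the patient has. The intercurrent-event rows of the 7.8.1 table give no strategy for amputation or intracerebral events; these are written into the target population instead.

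Section 12.1 uses a different group: "The treatment effect is the difference in the mean 30STS among participants who survive to 30 days follow-up under intervention and control". The synopsis says the same. Both state that the main analysis will be "conducted using multiple imputation under a missing at random assumption for those participants lost to follow-up", and both plan a delta-based sensitivity analysis.

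Section 7.8.2 describes the SACE as "estimating the average treatment effect in those patients who did not and would not die". Its table gives a principal stratum strategy to death and also to a row headed "New events that prevent the collection of the primary outcome". That row lists a new limb amputation, an intracerebral event that rules out function testing, and 'other'.

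Section 9.7.1 gives the test "scores ranging from 0 for those who cannot complete 1 stand to greater than 20 for more fit individuals". It adds: "The modified 30STS can be used for those unable to stand without the use of armrests". It also lists safety-screen answers after which a remote test is not done.

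**The concern.** An estimand fixes who the effect is for, and the analysis has to follow it. Here a survivor with a new stroke or amputation is outside the target population but inside the analysis population, and the protocol does not say which governs.

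The exclusion also needs a justification that the protocol does not give. Section 12.1 defends the comparison of survivors by assuming that neither feed affects mortality. It makes no such assumption for amputation or intracerebral events. These occur after randomisation, so removing the patients who have them conditions on a post-randomisation event, and the two remaining groups need not be comparable.

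Finally, 12.1 intends to check whether the SACE is consistent with the primary estimate. That check is informative about survival selection only if the two analyses treat the same non-fatal events alike, or if the difference is declared. As written, neither is the case.

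**Working it through.** **1. The four definitions side by side.**

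| Place | Who is removed besides the dead |
|---|---|
| 7.8.1, primary estimand | new amputation; any intracerebral event by day 30 |
| 12.1 and synopsis, primary analysis | nobody |
| 7.8.2, opening sentence | nobody |
| 7.8.2, table | new limb amputation; intracerebral event that precludes testing; 'other' |

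Take a participant who has an intracerebral event on day 12, survives, and can still do the test on day 30. This person is outside 7.8.1 and inside 12.1, and has no event under either part of 7.8.2. If the event prevents testing, the person is outside 7.8.1, inside 12.1, without an event under the 7.8.2 opening sentence, and has a truncating event under the 7.8.2 table. No single population fits all four places.

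**2. The plan's own figures.** Section 12.2 gives a difference of 2, SD 4.06, 90% power and 5% significance (taken as two-sided). The exact t calculation needs 88 per arm, 176 in total (power 0.901; 87 per arm gives 0.898). Inflation to 282 is reproduced by, for example, 176/(0.65 × 0.96) = 282.05. The sample size is not in dispute. It makes no allowance for survivors removed because of these events.

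**3. Shift in the mean difference.** Let q0 and q1 be the proportions of survivors unable to stand (control, ketogenic), and m0 and m1 the mean counts in those able.

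- Excluded: D = m1 − m0.
- Scored 0: D = (1 − q1)·m1 − (1 − q0)·m0.

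With equal means m, the two differ by (q1 − q0)·m in absolute size. Section 12.2 gives a mean of 5.98, so m ≈ 6. The imbalance is an assumption:

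- 2 points: 0.02 × 6 = 0.12 stands, 6% of the target of 2.
- 4 points: 0.04 × 6 = 0.24 stands, 12% of the target.

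For scale, 282 × 0.75 × 0.90 = 190 evaluable patients, so the standard error of the difference is about 4.06 × √(4/190) = 0.59. The larger shift is 0.24/0.59 ≈ 0.4 standard errors.

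With a true effect of 2 in those able (m0 = 5.98, m1 = 7.98), scoring 0 gives:

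- 5% unable in both arms: 0.95 × 2 = 1.9.
- 10% in both arms: 0.90 × 2 = 1.8.
- 10% control, 15% ketogenic: 0.85 × 7.98 − 0.90 × 5.98 = 1.4.
- 20% control, 10% ketogenic: 0.90 × 7.98 − 0.80 × 5.98 = 2.4.

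These rates are also assumed. They show the direction and sensitivity of the choice and do not estimate how often the two named events occur.

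**4. Precision if the 7.8.1 exclusion is applied.** Removing 2%, 5%, 10% or 15% of survivors (assumed) leaves 187, 181, 171 or 162 evaluable. Power falls from 0.922 to 0.917, 0.909, 0.894 or 0.876, without allowance for cross-over. At low event rates the loss is small.

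**The case against.** The best defence is that this is loose wording about rare events. The second sentence of the 7.8.2 text sends outcome-truncating events in general to a principal stratum strategy and leaves detail to the SAP, so its opening sentence may be shorthand. Read that way, 7.8.1 and the SACE table broadly agree, and 12.1 and the synopsis are the outliers. The illustrated shift is under half a standard error and rests on an assumed imbalance. It also compares exclusion with a zero score, whereas the conflict is between excluding these survivors and keeping them under no stated rule. All of this stands as a limit on size. It does not remove the conflict between 7.8.1 and 12.1, the difference between any intracerebral event and one that precludes testing, or the 'other' that appears only in the SACE table.

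Several stronger readings are tempting, but the protocol does not support them:

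- That the estimand excludes every survivor who cannot do the test. It excludes only those with the two named events; weak survivors stay in and can score 0.
- That a surviving stroke patient would be imputed as if able to stand. Section 12.1 states imputation only for those lost to follow-up. A followed-up but untestable survivor has no stated handling. If such patients were imputed at the able-patient means, the difference would stay near 2.0 in the illustration above.
- That the SACE cannot serve as a sensitivity analysis. It may target a different stratum by design; the fault is that the difference is undeclared and internally inconsistent.
- That armrest counts are pooled at face value and dilute the effect. Section 9.7.1 only permits the modified test and does not say how its count is used.
- That disabling harm disappears from the trial. It could leave the primary mean, but the Barthel Index, PICUPS and the win ratio can still register it.

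**Conclusion.** Wrong as written. The protocol defines two primary populations, and its SACE text and table do not match. The contradiction lies within the protocol, so it does not depend on what an SAP might add. Its numerical effect cannot be determined, because the protocol gives no rate for amputation or intracerebral events after randomisation. Under the assumed imbalance of 2 to 4 points and a mean near 6, the shift is modest. The case for correction rests on the primary estimand being undetermined and on the SACE comparison being hard to interpret, more than on a large expected bias. How armrest-modified and screened-out tests count is a linked but lesser gap.

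**What to change.** - Use one population and one event definition in 7.8.1, 7.8.2, 12.1 and the synopsis. Death by day 30 as the only truncating event is preferable, because it is the only event covered by the no-effect assumption in 12.1.
- Survivors physically unable to complete one stand, including after amputation or an intracerebral event, then score 0, which is where the test's own scale puts them: "scores ranging from 0 for those who cannot complete 1 stand".
- Treat survivors not assessed for other reasons as missing. State that the delta-based sensitivity analysis covers those stopped by the remote safety screen, since they may well do worse than those tested.
- Make the SACE text and table agree, and delete 'other'.
- Record the test version and the reason a test was not done. Before unblinding, fix how armrest-modified counts enter the endpoint, and run a sensitivity analysis under the alternative. Do not require a 0 for every armrest user: 9.7.1 expects many patients to find unaided standing difficult at critical care discharge, and such a rule could create a floor effect.

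If the sponsor prefers to keep the exclusion in 7.8.1, then 12.1, the synopsis and 7.8.2 must carry the same exclusion, with a justification for conditioning on these events.

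Cost: wording changes, one or two eCRF fields, and somewhat more zero scores. Scoring these survivors 0 also changes the estimand for them from exclusion to a composite of ability and event, which the sponsor should state openly.

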Given (i) 80% statistical power, (ii) a 10% alpha level, (iii) a trial sample size of 282 participants, (vi) a 75% 30-day survival probability in the control arm, (v) no survival difference between trial arms, and (vi) the proportional hazards assumption, the non-inferiority margin identified comprises a hazard ratio of 1.83 (HR=1.83). This equates to a 30-day survival probability non-inferiority margin of 0.59. A 10% alpha level is selected given that, for mortality, committing a Type I error is considered less concerning and identifying a difference between intervention and control arms if a difference truly exists is prioritised.

Table 1: Non-inferiority margins* identified for survival & binary outcomes

Outcome metric \geq	Statistical power	
	80%	90%
Survival outcome		
Hazard ratio (HR)	1.83	2.05
30-day survival probability	0.59	0.55
Binary outcome		
Absolute risk difference (ARD)	0.11	0.13

*Assuming a 10% alpha level, a trial sample size of 282 participants, a 75% 30-day survival probability,

no difference in survival between trial arms, and proportional hazards

A causal mediation analysis will be conducted to assess whether the effect of receiving the intervention treatment on the primary outcome is mediated through metabolite panels traits considered as Principal Components.⁷⁹ The traits included in the panel will be determined in the mechanistic outcomes analysis. Participant baseline characteristics will be summarised using suitable descriptive statistics for central tendency and variability.

An unmatched win ratio approach will be used as a secondary analysis to assess net clinical benefit. The win ratio treatment effect will be estimated using hierarchically (in this order) the outcomes 30-day mortality (yes/no), 30STS, and Barthel Index 30 days after randomisation. More emphasis will be placed on the win ratio analysis if relevant differences in mortality are observed. A full statistical analysis plan will be prospectively developed.

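### The mortality non-inferiority margin (hazard ratio 1.83) was solved from the sample size, so a pass cannot show that mortality is unaffected by feed, as the survivor-only primary analysis assumes

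*Protocol*

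**What the plan says.** Protocol section 12.1 makes the primary analysis a comparison of the 30-second sit-to-stand count among 30-day survivors. For that analysis "it is assumed that neither feeding regimen influences mortality in the population of interest". The section cites outside trial evidence in support, concedes that the question is debated, and then says mortality will be monitored by the DMEC and formally assessed at the end by a non-inferiority test.

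The inputs to the margin are listed as givens: "Given (i) 80% statistical power", "ii) a 10% alpha level", 282 participants, "a 75% 30-day survival probability in the control arm", no true difference, and proportional hazards. From these, "the non-inferiority margin identified comprises a hazard ratio of 1.83 (HR=1.83). This equates to a 30-day survival probability non-inferiority margin of 0.59". Table 1 gives a second hazard ratio margin, 2.05 (survival 0.55), for 90% power. It also gives absolute risk differences of 0.11 and 0.13 for a binary outcome.

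Section 12.2 derives the 282 from the sit-to-stand outcome (2 repetitions, SD 4.06, 90% power, 5% significance, then inflation). Mortality enters only as an inflation factor.

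**The concern.** A non-inferiority margin should say how much excess mortality would be tolerable. Here the sample size, power and alpha come first and the margin is their output. That is why Table 1 can give one margin per power level, which a margin fixed on clinical grounds would not do. The section offers no argument that a hazard ratio of 1.83 is acceptable.

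This bears on the primary result because that analysis conditions on survival. If one feed caused extra deaths among weaker patients, its survivors would look stronger without any functional benefit. If it prevented such deaths, its survivors would look weaker. The only formal check on mortality is one-sided against a wide margin, so it does not test whether the two survivor groups are comparable.

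**Working it through.** **Inputs.** Control survival 0.75, N = 282 at 1:1 (141 per arm, section 9.4), power 80% or 90%, alpha 10% with sidedness not stated, SD 4.06 and target 2 stands (section 12.2). Expected deaths with no effect: 282 × 0.25 = 70.5, or 36 per arm = 72 if rounded up by arm.

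**Reproducing the margin.** Freedman's formula solved for the hazard ratio is HR = (r + 1)/(r − 1), with r = √events/(z_alpha + z_power). With 72 events and one-sided 5% (10% two-sided):
- 80% power: r = 8.485/2.486 = 3.413, HR = 4.413/2.413 = 1.829
- 90% power: r = 8.485/2.926 = 2.900, HR = 3.900/1.900 = 2.053

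These match 1.83 and 2.05, so the margin follows from N. Read as one-sided 10%, the 80%-power value would be about 1.66 to 1.68.

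**What the margin allows.** 0.75^1.83 = 0.591, so mortality at the boundary is 40.9% against 25%, a rise of 15.9 points.

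**What would pass.** The test passes if ln(observed HR) + z_alpha × 2/√events < ln 1.83. With 70.5 to 80.4 events:
- one-sided 5%: observed HR up to about 1.24 to 1.27 (mortality about 30-31%)
- one-sided 10%: observed HR up to about 1.35 to 1.38 (mortality about 32-33%)

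**Chance of a pass under a true excess.** Illustration: 25% against 32%. True HR = ln 0.68/ln 0.75 = 1.341; expected deaths = 141 × (0.25 + 0.32) = 80.4. P(pass) = Φ[(ln 1.83 − ln 1.341) × √events/2 − z_alpha], where ln 1.83 − ln 1.341 = 0.311.
- 80.4 events: Φ(1.395 − 1.645) = 0.40 at one-sided 5%; Φ(1.395 − 1.282) = 0.55 at one-sided 10%
- 70.5 events: Φ(1.307 − 1.645) = 0.37; Φ(1.307 − 1.282) = 0.51

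At a true HR of 1.83 the bracket is zero, so the pass rate is alpha itself: 5% or 10%.

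**Effect on the survivor comparison.** A 7-point excess removes a share p = 0.07/0.75 = 0.093 of those who would otherwise survive. Assume no true functional effect and about 141 × 0.75 × 0.90 = 95 analysed per arm, so SE = 4.06 × √(2/95) = 0.589. The false-superiority rate is Φ(bias/0.589 − 1.96), which is 2.5% without bias.
- Milder case, in which those removed average 3 stands below the rest (my assumption): bias = 3 × 0.093 = 0.28 stands; Φ(0.475 − 1.96) = about 7%
- Worst case, in which only the weakest die and scores are normal: bias = 4.06 × φ(z_p)/(1 − p) = about 0.75 stands; Φ(1.273 − 1.96) = about 25%

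**What 282 patients can say.** With 25% mortality in both arms, the SE of the risk difference is √(2 × 0.75 × 0.25/141) = 0.0516, so a two-sided 95% interval spans about ±10 points. For illustration only, a 5-point margin would have Φ(0.05/0.0516 − 1.282) = 38% power at one-sided 10%.

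**The case against.** A reader might infer that the test would accept an observed rise from 25% to 41%. It would not. 41% is the null boundary: an observed 41% fails, and a true 41% passes only at the alpha rate. An observed excess that passes is about 5 to 8 points.

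A reader might also infer that a harmful feed would often be reported as both non-inferior on mortality and better on function. That needs both errors together. Treating them as roughly independent, the 7-point excess gives 0.40 × 0.07 to 0.55 × 0.07, or 3-4%, in the milder case. In the worst case it gives 0.40 × 0.25 to 0.55 × 0.25, or 10-14%. The worst case requires that only the very weakest die.

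Nor does the protocol say that a pass will be cited as validating the survivor analysis. It rests that assumption on outside evidence and says only that mortality will be formally assessed.

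The sentence "More emphasis will be placed on the win ratio analysis if relevant differences in mortality are observed" could be read as letting the lead analysis be chosen once deaths are known. But the primary analysis is fixed, the win ratio is labelled secondary and ranks death first, and what counts as relevant can be defined in the statistical analysis plan.

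The protocol also commits to a survivor average causal effect analysis (section 7.8.2), 30- and 90-day mortality as secondary outcomes (section 7.5), and DMEC review with early termination for harm (section 20.3). All of this stands and softens the consequence.

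Finally, Table 1 holds a tighter binary margin of 0.11 (mortality 36%), under which a true 7-point excess passes about 30% of the time at one-sided 10%. But 0.11 is also an output of N: (1.282 + 0.842) × 0.0516 = 0.1095. The text names 1.83 as the margin. None of these points supplies a reason why 1.83 is tolerable.

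**Conclusion.** The point holds for the margin. HR 1.83 is reproduced from 282 patients, has no clinical justification in the protocol, and classes any true 30-day mortality from 25% up to just under 41% as non-inferior. A true 25% against 32% would be declared non-inferior about 37-40% of the time at one-sided 5%, or 51-55% at one-sided 10%. A pass is therefore compatible with a mortality effect large enough to disturb the survivor comparison: about 0.28 stands in the milder case and 0.75 in the worst, against a target of 2. A mortality reduction is not addressed at all.

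These sizes rest on 25% control mortality, proportional hazards, a 7-point excess chosen for illustration, 10% loss to follow-up, and the two stated assumptions about who dies. That the margin comes from N depends on none of the last three. The sit-to-stand sample size and the primary model are unaffected.

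**What to change.** In section 12.1 and in the statistical analysis plan:
- Do not use HR 1.83 or 2.05 as a decision threshold.
- Either report 30- and 90-day mortality risk differences, and the hazard ratio, with two-sided 95% confidence intervals, and state that 282 patients cannot exclude an important mortality excess; or set a margin on clinical grounds before unblinding and state the power the trial actually has for it.
- State that a non-inferiority pass is not evidence for the assumption that feed does not affect mortality.
- Present the survivor estimate alongside the survivor average causal effect and win ratio analyses already planned.

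The cost is wording. The sponsor gives up a statement of non-inferior mortality that the trial cannot support. No extra patients or data are needed.

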9.4 Randomisation procedures

A bespoke web-based system with 24-hour availability will be developed for randomisation. Randomisation will use a 1:1 allocation ratio between arms and be stratified by site. Random permuted blocks of sizes 4 and 6 will be used within strata.

Patients will be randomised by a delegated member of the research team. The database is accessible via the NHS computers on site, with access only given to delegated members of the research team. Following randomisation, confirmation e-mail will be sent to the member of the research team randomising. This will be included in the patient's medical records and in the ISF.

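### The 10% alpha for the mortality non-inferiority test rests on the logic of a test for difference: at a given margin it makes missed harm more likely, and Table 1 mixes two readings of that alpha

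*Protocol*

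**What the plan says.** Protocol section 12.1 states that mortality will be "formally assessed at the end of the trial using a non-inferiority test". It then solves for a margin from six inputs, among them "i) 80% statistical power", "ii) a 10% alpha level", "iii) a trial sample size of 282 participants", 75% control survival at 30 days and no true survival difference. The answer is a hazard ratio of 1.83, equivalent to 30-day survival of 0.59 against 0.75.

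The reason for the alpha is given as follows: "A 10% alpha level is selected given that, for mortality, committing a Type I error is considered less concerning". The same sentence puts the detection of a real difference between the arms first.

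Table 1 lists margins at 80% and 90% power: HR 1.83 and 2.05 for the survival outcome, absolute risk difference 0.11 and 0.13 for the binary outcome. Its footnote applies one alpha to both rows ("Assuming a 10% alpha level, a trial sample size of 282 participants, a 75% 30-day survival probability") and does not say whether it is one-sided or two-sided.

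**The concern.** The named test and the reason given for its alpha do not fit together. In a test of difference the null is equal mortality, a Type I error is a false alarm, and a lenient alpha makes a real difference easier to find. In a non-inferiority test the null is that the ketogenic arm is worse by at least the margin. A Type I error is then a declaration of non-inferiority when mortality really is that much worse. Power, which the protocol computes under equal survival, is the chance of declaring non-inferiority when the arms are equal, not the chance of finding a difference. Relaxing alpha therefore gives up the protection that the sentence says it prioritises.

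The result also bears on the primary analysis. Section 12.1 compares survivors on the assumption that neither feed influences mortality. A non-inferiority verdict reached too easily would lend that assumption support it has not earned.

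**Working it through.** **Inputs.** From section 12.1: N = 282, control survival 0.75, power 80% or 90%, alpha 10%, no true difference. From section 9.4: 1:1 allocation, so 141 per arm. Expected deaths under equal survival: 282 × 0.25 = 70.5, or 72 if 35.25 per arm is rounded up to 36.

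**Reproducing the hazard ratio row.** Freedman: HR = (1 + x)/(1 − x), with x = (z_alpha + z_power)/√D and D = 72.

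- 10% two-sided (z = 1.645), 80% power: x = (1.645 + 0.842)/8.485 = 0.293, HR = 1.829. At 90% power: x = 0.345, HR = 2.053. These match 1.83 and 2.05.
- 10% one-sided (z = 1.282): HR = 1.667 and 1.866. These do not match.

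**Reproducing the risk difference row.** Margin = (z_alpha + z_power) × √(2 × 0.25 × 0.75/141) = (z_alpha + z_power) × 0.0516.

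- 10% one-sided: 0.1095 and 0.132. These match 0.11 and 0.13.
- 10% two-sided (5% one-sided): 0.128 and 0.151. These do not match.

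So the two rows of Table 1 use different error rates under one label.

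**Effect of alpha at a fixed margin of HR 1.83.** Schoenfeld approximation with D = 70.5, so √D/2 = 4.198:

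P(declare non-inferiority) = Φ(4.198 × [ln 1.83 − ln HR] − z)

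Largest observed HR that passes = 1.83/exp(z/4.198)

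Mortality implied by a hazard ratio = 1 − 0.75^HR.

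| One-sided alpha | True HR 1.83 (41% vs 25%) | True HR 1.5 (35% vs 25%) | True HR 1.0 (power) | Largest observed HR that passes |
|---|---|---|---|---|
| 2.5% | 2.5% | 13% | 72% | 1.15 |
| 5% | 5% | 21% | 81% | 1.24 |
| 10% | 10% | 33% | 90% | 1.35 |

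For example, at true HR 1.5: 4.198 × ln(1.83/1.5) = 0.835. Subtracting 1.960, 1.645 and 1.282 gives −1.125, −0.810 and −0.447, hence 13%, 21% and 33%. If the deaths expected under HR 1.5 (84.7) are used instead of 70.5, the figures are about 15%, 23% and 36%.

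**What happens if the margin is re-solved.** With N and 80% power held fixed, margin = exp((z_alpha + 0.842)/4.198): 1.95 at one-sided 2.5%, 1.81 at 5% and 1.66 at 10%. The largest observed HR that passes is then exp(0.842/4.198) = 1.22 at every alpha.

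**Where a lenient alpha does help.** In a one-sided test of excess mortality with a no-difference null, power at true HR 1.5 is Φ(4.198 × ln 1.5 − z) = Φ(1.702 − z): 40%, 52% and 66% at one-sided 2.5%, 5% and 10%. Here a larger alpha does raise the chance of finding harm, which is what the protocol's sentence describes.

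**The case against.** Three arguments on the other side carry weight.

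First, a reader might infer that the HR 1.83 test runs at a one-sided error of 10%, four times the usual 2.5%. The documents do not support that. One-sided 10% would give about 90% power at HR 1.83, and the protocol states 80%. Only 10% two-sided reproduces the hazard ratio row, so for that row the contrast is 5% against 2.5%, with the largest passing HR at 1.24 against 1.15. The 10% figures fit the risk difference row only.

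Second, the margin is an output of the calculation. Under the protocol's own recipe a larger alpha gives a smaller margin, and the observed result that passes does not move. A reader might infer that lowering alpha is enough to restore protection. It is not: re-solving at one-sided 2.5% would widen the margin to about 1.95. The statement that a larger alpha weakens protection holds only at a given margin.

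Third, a reader might infer that this test is the sole safeguard on mortality. It is not. Section 7.2 plans inference on the mortality difference, sections 12.1 and 20.3 provide for committee monitoring with early termination for harm, section 7.8.2 adds a survivor average causal effect analysis, and the win ratio ranks 30-day mortality first. Mortality is a secondary outcome, and no stated rule makes the primary analysis depend on this test. Nor does anything in the protocol require one-sided 2.5%; one-sided 5% with a correct rationale would also be coherent.

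These points limit the size of the problem and shape the remedy. None of them makes the stated rationale correct.

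**Conclusion.** The rationale is wrong as written. It justifies the alpha of a non-inferiority test by the error structure of a test of difference, and so relaxes the error that guards against accepting excess mortality. The protocol also leaves sidedness open and uses two different error rates in one table.

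The size depends on which row is used. For the hazard ratio row, against a conventional one-sided 2.5%, the chance of accepting a true HR of 1.83 is 5% instead of 2.5%, and of accepting a true HR of 1.5 about 21% instead of 13%. If one-sided 10% were applied to that margin, the figures would be 10% and 33%. They rest on proportional hazards, 25% control mortality, about 70.5 deaths and a margin held at 1.83.

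The point deserves correction because this is the only mortality test whose alpha and margin are specified, and because it touches the no-mortality-effect assumption behind the survivor analysis.

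**What to change.** 1. Delete the sentence that explains the 10% alpha.
2. State a one-sided alpha and use it for both rows of Table 1. One-sided 2.5% is the usual choice.
3. Fix the margin and justify it on its own grounds, instead of re-solving it from sample size, power and alpha.
4. Report the power that results. Against HR 1.83 it is about 72% at one-sided 2.5% and about 81% at one-sided 5%.
5. If the aim is sensitivity to harm, specify instead a test of excess mortality with a no-difference null, where a lenient alpha does serve the stated purpose.

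The cost is a change of wording in the protocol, carried into the SAP, and a lower stated power. No extra patients are needed.
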